Appendix 6. Performance Status Scoring System (ECOG)

Grade	ECOG
0	Fully active, able to carry on all pre-disease performance without restriction
1	Restricted in physically strenuous activity but ambulatory and able to carry out work of a light or sedentary nature, e.g., light house work, office work
2	Ambulatory and capable of all self-care but unable to carry out any work activities. Up and about more than 50% of waking hours
3	Capable of only limited self-care, confined to bed or chair more than 50% of waking hours
4	Completely disabled. Cannot carry on any self-care. Totally confined to bed or chair
5	Dead

Appendix 7. RECIST 1.1

E.A. Eisenhauer, et al. New response evaluation criteria in solid tumors:

Revised RECIST guideline (version 1.1). European Journal of Cancer 45 (2009) 228-247.

Appendix 8. Exemestane (Aromasin®) Prescribing Information

[http://www\(pfizer.com/products/product-detail/aromasin](http://www(pfizer.com/products/product-detail/aromasin)

Appendix 9. Fulvestrant (Faslodex[®]) Prescribing Information

<http://www.faslodexhcp.com/home.html>

Appendix 10. Bayesian Logistic Regression Model

Determination of the MTD will be based on the posterior probability of DLT rate estimated by a 2-parameter BLRM with overdose control {[Neuenschwander 2008](#)} and calculated using East software {[Cytel Inc 2016](#)}.

Let $\pi[d_i]$ be the probability of DLT at dose level d_i of GS-5829. The statistical model describing dose-toxicity relationship will have the following form:

$$\pi[d_i] = \frac{\exp(\log(\alpha) + \beta \log(\frac{d_i}{d^*}))}{1 + \exp(\log(\alpha) + \beta \log(\frac{d_i}{d^*}))}$$

where $\alpha, \beta > 0$ and d^* is the reference dose level. The prior specification of the model parameters is provided below. The estimate of parameters will be updated as data are accumulated and the toxicity probability at each dose level will be calculated based on the posterior distributions of the model parameters. The estimated posterior probability of DLT rate at each dose level will be summarized using the following intervals:

Under dosing: [0.00, 0.167)

Targeted toxicity: [0.167, 0.333]

Excessive toxicity: (0.333, 1.00]

The overdose control criterion is set as the posterior probability of excessive toxicity less than 25%. The dose level recommended for the next cohort will be the dose cohort at which the posterior probability for the target toxicity interval is maximum among all dose candidates satisfying the overdose control criterion.

The trial can be stopped if any one of three criteria is met:

1. The posterior probability of targeted toxicity exceeds 70% and at least 6 subjects have been allocated at a dose level
2. Maximum number of subjects (N=12) has been treated at a dose level
3. Maximum number of subjects (N=30) has been reached

1. Planned Dose Levels

The provisional dose levels for GS-5829 are 3 mg, 4 mg, 6 mg and 9 mg once daily.

2. Prior Specification

The prior distribution for $(\log(\alpha), \log(\beta))$ is assumed to be a bivariate normal distribution. The following non-informative prior is used first:

- The median DLT rate at 3 mg is assumed to be 15%, i.e. $\text{mean}(\log(\alpha)) = -1.73$.
- A doubling in dose is assumed to double the odds of DLT, i.e. $\text{mean}(\log(\beta)) = 0$
- The StD of $\log(\alpha)$ is set to 2 and the StD of $\log(\beta)$ to 1.
- The correlation between $\log(\alpha)$ and $\log(\beta)$ is set to be 0.

Then the posterior is calculated based on the data collected from other on-going studies (GS-US-350-1599 and GS-US-350-1604) and will be updated as more data in these studies are collected. The prior for the current study will be based on the posterior calculated based on the data from GS-US-350-1599 and GS-US-350-1604 with inflated variance to discount the information from GS-US-350-1599 and GS-US-350-1604 considering between-trial variations.

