Appendix Table 4. True underlying DLT rates in hypothetical scenarios

QD Dose (mg)	True DLT rate	
	Scenario 1	Scenario 2
2	0.30	0.10
3	0.40	0.20
4	0.50	0.30
6	0.60	0.40
9	0.70	0.50

As shown in [Appendix Table 5](#), the simulations illustrate that the model has reasonable operating characteristics. The probabilities of recommending a correct dose level and stopping the study with declaring all dose levels to be toxic are 27.9% and 53.1%, respectively, in Scenario 1. The probability of recommending a correct dose level in Scenario 2 is 73.8%. The design is not aggressive to assign subjects to high toxic dose levels even with strong prior information based on the safety data from 20 evaluable subjects from other studies as of July 22, 2016.

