Appendix Table 5. Simulation results for operating characteristics in hypothetical scenarios

Operating Characteristics	Scenario 1	Scenario 2
Proportion of trials that recommend dose levels with true $\Pr(\text{DLT})$ in $[0.167, 0.333]$ (Correct decision)	27.9%	73.8%
Proportion of trials that recommend dose levels with true $\Pr(\text{DLT}) > 0.333$ (Patient risk)	19.0%	13.7%
Proportion of trials that recommend dose levels with true $\Pr(\text{DLT}) < 0.167$	0	3.6%
Proportion of trials which stops early because all dose levels are too toxic	53.1%	8.9%
Average number of subjects evaluated	15	20

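### Appendix 10 reports early stopping because all doses are too toxic, but its written rules do not say what happens when no planned dose is admissible, and the figures come from a different dose grid

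*Protocol*

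**What the plan says.** Appendix 10 of the protocol defines the dose-finding rules. The next dose is the one whose probability of lying in the target toxicity interval is "maximum among all dose candidates satisfying the overdose control criterion", where that criterion is a posterior probability below 25% that the DLT rate exceeds 33.3%. On stopping, the appendix says "The trial can be stopped if any one of three criteria is met". In short, these are:

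1. a precision stop, when a dose with 6 or more subjects has a target-interval probability above 70%;
2. a cap of 12 subjects at any one dose;
3. a cap of 30 subjects in total.

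The planned levels are 3, 4, 6 and 9 mg.

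The operating characteristics in the same appendix were simulated on 2, 3, 4, 6 and 9 mg (Appendix Table 4). Appendix Table 5 has a row "Proportion of trials which stops early because all dose levels are too toxic", with 53.1% in Scenario 1 and 8.9% in Scenario 2. The accompanying text repeats the Scenario 1 figure and concludes that the model performs reasonably.

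The Synopsis and Section 3.2 repeat the 25% limit and give the escalation decision to the SRT. They say that Group B escalation runs until an MTD is identified or an RP2D is reached. Neither says what happens when no dose meets the limit.

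**The concern.** The first listed criterion stops the trial for precision, and the other two stop it for size. None responds to excess toxicity. If every planned level fails the 25% limit, the next-dose rule takes a maximum over an empty set and returns nothing. The SRT is told to review the model recommendation, but there is then no recommendation to review and no listed reason to stop.

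The simulations treat that same situation as a defined end of the trial, and in Scenario 1 it is the most common one. The conclusion about operating characteristics therefore depends on a step that the written rules omit. The omission applies where early cohorts are most toxic, so the protocol should be explicit there. The simulated grid also has a lower bottom level than the trial, so the reported stopping rates do not describe the planned design even if the missing step is supplied.

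**Working it through.** **Inputs.** All are from Appendix 10 unless noted.
- Model: logit of the DLT probability at dose d = log(alpha) + beta × log(d / reference dose).
- Reference dose: 3 mg. This is inferred, because the stated 15% median DLT rate at 3 mg corresponds to logit(0.15) = −1.73, the printed prior mean of log(alpha).
- Simulation prior (Appendix Table 2): means (−2.13, 0.52), variances (1.12, 2.04), correlation −0.01 for (log alpha, log beta).
- Cohorts of 3 and a starting dose of 4 mg (Section 3.2).

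**Model check.** A grid posterior from the first-stage prior and the DLT data in Appendix Table 1 gives means −2.15 and 0.49 (printed −2.13 and 0.52) and variances 0.58 and 1.00 (printed 0.56 and 1.02). The model is therefore the protocol's, to within small numerical differences.

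**Table 5 accounting.** The outcome rows are exhaustive:
- Scenario 1: 27.9 + 19.0 + 0 + 53.1 = 100.0%.
- Scenario 2: 73.8 + 13.7 + 3.6 + 8.9 = 100.0%.

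The toxicity stop is thus a separate way for a trial to end.

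**Can the state occur under the written rules?** Start at 4 mg with the simulation prior.
- After 2 DLTs in 3 subjects at 4 mg, the probability of excessive toxicity is 0.21 at 3 mg and 0.69 at 4 mg, so 3 mg is the only admissible planned level.
- After a further 2 DLTs in 3 subjects at 3 mg:

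| Dose | P(excessive) | P(target) | Below 25% limit? |
|---|---|---|---|
| 2 mg (simulated, not planned) | 0.23 | 0.30 | yes |
| 3 mg | 0.53 | 0.37 | no |
| 4 mg | 0.85 | 0.14 | no |
| 6 mg | 0.93 | 0.07 | no |
| 9 mg | 0.96 | 0.04 | no |

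No planned level is admissible. Against the three criteria, the largest planned-level target probability is about 0.37 (needs more than 0.70) with 3 subjects at each dose (needs at least 6), no dose has 12 subjects, and the total is 6, not 30. None is met. On the simulated grid 2 mg still qualifies, so an all-doses-too-toxic stop would not have fired on the same data.

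**What produces a figure like 53.1%?** The design was simulated with 3,000 to 5,000 trials per variant, varying the start dose (2, 3 or 4 mg), whether doses may be skipped, and whether the stopping criteria are checked at the current or the next dose.
- On the 2–9 mg grid with an added rule that the trial stops when no dose is admissible, 46.5% to 55.6% of Scenario 1 trials stop for toxicity. This brackets 53.1%.
- With only the three listed criteria the figure is 0%, because no listed criterion is a toxicity stop.
- In Scenario 2 the added rule gives 2.4% to 4.9%, against the printed 8.9%, so Table 5 is not fully reproduced.
- On the planned 3–9 mg grid under the Scenario 1 rates, 72% to 79% of trials reach a point with no admissible dose.

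**Sensitivity to the prior.** Appendix 10 says the prior will be updated. Section 1.3.1 reports later monotherapy data: 9 evaluable subjects at 4 mg, with one DLT there and one at 3 mg. Refitting with those data and then applying the same six subjects gives an excess-toxicity probability at 3 mg of 0.42 if the variances are doubled (an assumption that mirrors Appendix Table 2), and 0.12 if they are not. The example holds in the first case and not in the second.

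**The case against.** The strongest reply is that the protocol does control overdosing. Every recommendation is limited to doses below the 25% threshold, in Appendix 10, the Synopsis and Section 3.2. If none qualifies, the model can recommend none, and the operating-characteristics text describes that outcome as stopping with all levels declared toxic. The listed criteria are permissive, the SRT decides on all the data, and Section 9.3.4 lets the sponsor terminate at any time.

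Most of this stands. A reader might infer that the design has no protection against overdosing, and the documents do not support that. What remains is that the intended action has to be deduced from a results table, and that a general right to terminate is not an escalation rule.

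Three other stronger readings also go too far:
- A reader might take it as established that Table 5 was run with a fourth rule. That is likely, but it is an inference: the simulation's start dose, step rules and stopping rules are not stated, and Scenario 2 does not reproduce.
- A reader might suppose that writing in the simulated rule would settle the matter. It would not, because the same rule behaves differently on 3–9 mg than on 2–9 mg, as the six-subject example shows.
- A reader might think the protocol claims a low rate of recommending toxic doses. It does not. Table 5 prints 19.0% in Scenario 1, which is 19.0 / (100 − 53.1) = 41% of the trials that recommend any dose.

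**Conclusion.** The point holds as a gap between the written rules and the reported operating characteristics, not as absent overdose control. The stop behind 53.1% (Scenario 1) and 8.9% (Scenario 2) of simulated trials appears in none of the three listed criteria or the SRT text, and those percentages belong to a grid with a 2 mg level that the trial does not plan to use.

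Under the printed simulation prior the undefined state can be reached after six subjects. How readily it arises depends on the prior in force, on the inferred 3 mg reference dose and, for the simulated rates, on rules that the protocol does not give.

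Section 1 of the SAP records that the sponsor discontinued the study during dose escalation, so the consequence is for the documented design and its stated performance. It should be corrected because it bears on safety decisions, but it does not show that any subject was dosed outside the overdose limit.

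**What to change.** State in Appendix 10, and in matching words in the Synopsis and Section 3.2, what the SRT does when no planned level meets the overdose criterion. The choice of rule belongs to the sponsor. The requirement is that it be written and agree with what is simulated.

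Then rerun the simulations on 3, 4, 6 and 9 mg with the stopping, start-dose and step rules as written, state those rules beside the results, and restate Appendix Tables 4 and 5 and the conclusion drawn from them. If 2 mg is meant to be available as an escalation level, the planned levels and the simulated grid must be reconciled the other way.

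The cost is a short text edit plus a simulation rerun. The printed figures may change: the toxicity-stop proportion in Scenario 1 could be well above 53.1% on the planned grid.

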Appendix Table 1. DLT data collected in GS-US-350-1599 and GS-US-350-1604 as of 22 July 2016*

QD Dose (mg)	Total number of evaluable subjects	Number of subjects with DLT
0.6	2	0
1.4	1	0
2	5	0
3	10**	1
4	2	1

* Current data were collected only for subjects with GS-5829 monotherapy

** A total of 13 subjects dosed, but 10 were evaluable

Appendix Table 2. Prior for and Posterior from current data collected in GS-US-350-1599 and GS-US-350-1604

Parameter	Means	Variances	Correlation
Prior for $(\log(\alpha), \log(\beta))$	(-1.73, 0)	(4, 1)	0
Posterior for $(\log(\alpha), \log(\beta))$ from data in Appendix Table 1	(-2.13, 0.52)	(0.56, 1.02)	-0.01
Prior for $(\log(\alpha), \log(\beta))$ used to assess operating characteristics by simulation	(-2.13, 0.52)	(1.12, 2.04)	-0.01

Appendix Table 3 shows the posterior probabilities of DLT rate based on current data from GS-US-1599 and GS-1604. Because there is a high chance of under dosing for 2 mg and low chance of overdosing for 3 mg, 3 mg once daily of GS-5829 is planned as the starting dose in the Phase 1b Dose Escalation portion of this study. The starting dose level may be either higher or lower than 3 mg once daily, if either a higher or lower dose has been demonstrated to be both safe and tolerable in Studies GS-US-350-1599 and GS-US-250-1604. The new dose level will be selected prior to initiating dosing in this study.

Appendix Table 3. Summary of posterior probabilities of DLT based on data from GS-US-350-1599 and GS-US-350-1604 as of 22 July 2016

QD Dose (mg)	Pr(DLT)	Posterior Probability of		
		Median	Under [0%, 16.7%]	Target [16.7% 33.3%]
2	0.05	0.95	0.05	0.001
3	0.10	0.68	0.30	0.02
4	0.2	0.43	0.35	0.23
6	0.34	0.24	0.26	0.50
9	0.51	0.15	0.20	0.65

3. Operating Characteristics

In order to assess operating characteristics, simulation was performed under 2 hypothetical scenarios using East software {Cytel Inc 2016}. A total of 1000 trials were simulated under each scenario.

Scenario 1: Only the lowest dose level (2 mg) is safe

Scenario 2: The dose level of 4 mg or below are safe

Appendix Table 4. True underlying DLT rates in hypothetical scenarios

QD Dose (mg)	True DLT rate	
	Scenario 1	Scenario 2
2	0.30	0.10
3	0.40	0.20
4	0.50	0.30
6	0.60	0.40
9	0.70	0.50

As shown in [Appendix Table 5](#), the simulations illustrate that the model has reasonable operating characteristics. The probabilities of recommending a correct dose level and stopping the study with declaring all dose levels to be toxic are 27.9% and 53.1%, respectively, in Scenario 1. The probability of recommending a correct dose level in Scenario 2 is 73.8%. The design is not aggressive to assign subjects to high toxic dose levels even with strong prior information based on the safety data from 20 evaluable subjects from other studies as of July 22, 2016.

Appendix Table 5. Simulation results for operating characteristics in hypothetical scenarios

Operating Characteristics	Scenario 1	Scenario 2
Proportion of trials that recommend dose levels with true $\Pr(\text{DLT})$ in $[0.167, 0.333]$ (Correct decision)	27.9%	73.8%
Proportion of trials that recommend dose levels with true $\Pr(\text{DLT}) > 0.333$ (Patient risk)	19.0%	13.7%
Proportion of trials that recommend dose levels with true $\Pr(\text{DLT}) < 0.167$	0	3.6%
Proportion of trials which stops early because all dose levels are too toxic	53.1%	8.9%
Average number of subjects evaluated	15	20

## LIST OF ABBREVIATIONS

AE	adverse event
AEI	adverse event of interest
ALT	alanine aminotransferase
AST	aspartate aminotransferase
BLQ	below the limit of quantitation
BMI	body mass index
BOR	best overall response
CBR	clinical benefit rate
CI	confidence interval
CR	complete response
CRF	case report form
CSR	clinical study report
CTCAE	Common Terminology Criteria for Adverse Events
DLT	dose-limiting toxicity
ECG	electrocardiogram
ET	early termination
FAS	Full Analysis Set
HLT	high-level term
HR	heart rate
KM	Kaplan-Meier
LT	lower-level term
LOQ	limit of quantitation
MedDRA	Medical Dictionary for Regulatory Activities
MST	medical search term
MTD	maximum tolerated dose
NE	not evaluable
ORR	overall response rate
PD	progressive disease
PFS	progression-free survival
PK	pharmacokinetics
PR	partial response
PT	preferred term
PVE	Pharmacovigilance and Epidemiology
Q1, Q3	first quartile, third quartile
QRS	electrocardiographic deflection between the beginning of the Q wave and termination of the S wave representing time for ventricular depolarization
QT	electrocardiographic interval between the beginning of the Q wave and termination of the T wave representing the time for both ventricular depolarization and repolarization to occur
QTc	QT interval corrected for heart rate
QTcF	QT interval corrected for heart rate using Fridericia's formula

RR	electrocardiographic interval representing the time measurement between the R wave of one heartbeat and the R wave of the preceding heartbeat
SAE	serious adverse event
SAP	statistical analysis plan
SD	stable disease
StD	standard deviation
SMQs	standardised MedDRA queries
SOC	system organ class
TEAE	treatment-emergent adverse event
TFLs	tables, figures, and listings
ULN	upper limit of normal
WHO	World Health Organization

## PHARMACOKINETIC ABBREVIATIONS

AUC last	area under the concentration versus time curve from time zero to the last quantifiable concentration
AUC tau	area under the concentration versus time curve over the dosing interval
%AUC exp	percentage of AUC extrapolated between AUC last and AUC inf
AUC x-xx	partial area under the plasma/serum concentration versus time curve from time “x” to time “xx”
C last	last observed quantifiable concentration of the drug
C max	maximum observed concentration of drug
C tau	observed drug concentration at the end of the dosing interval
CL ss/F	apparent clearance after non-intravenous administration of the drug: after a single dose: $CL/F = Dose/AUC_{inf}$ ; at steady state: $CL_{ss}/F = Dose/AUC_{tau}$ , where “Dose” is the dose of the drug
V z/F	apparent volume of distribution during terminal phase after non-intravenous administration of the drug
t 1/2	estimate of the terminal elimination half-life of the drug, calculated by dividing the natural log of 2 by the terminal elimination rate constant ( $\lambda_z$ )
T last	time (observed time point) of C last
T max	time (observed time point) of C max
$\lambda_z$	terminal elimination rate constant, estimated by linear regression of the terminal elimination phase of the concentration of drug versus time curve

## 1. INTRODUCTION

This statistical analysis plan (SAP) describes the statistical analysis methods and data presentations to be used in tables, figures, and listings (TFLs) of the final analysis for Study GS-US-350-1937. This SAP is based on the study protocol Amendment 2.2 dated 20 November 2017 and the electronic case report form (eCRF). The SAP will be finalized prior to data finalization for the final analysis. Any changes made after the finalization of the SAP will be documented in the clinical study report (CSR).

The study protocol included two phases in the design: phase 1b dose escalation and randomized phase 2 dose expansion. The study was discontinued during the dose escalation phase based on sponsor decision without moving forward to the randomized phase 2 dose expansion. All subjects who were enrolled in phase 1b have discontinued study drug and conducted the safety follow-up visit.

### 1.1. Study Objectives

The primary objectives are as follows:

#### **Phase 1b Dose Escalation:**

- To characterize the safety and tolerability of GS-5829 in combination with fulvestrant and exemestane in subjects with advanced estrogen receptor positive, HER2 negative breast cancer (ER+/HER2- BrCa)
- To determine the Maximum Tolerated Dose (MTD), or the recommended Phase 2 Dose (RP2D) of GS-5829 in combination with fulvestrant in subjects with advanced ER+/HER2- BrCa

#### **Randomized Phase 2 Dose Expansion:**

To evaluate the efficacy of GS-5829 in combination with fulvestrant compared to fulvestrant alone in subjects with advanced ER+/HER2- BrCa as measured by progression-free survival (PFS).

The secondary objectives are as follows:

#### **Phase 1b Dose Escalation**

- To evaluate the pharmacokinetics of GS-5829 in combination with fulvestrant in subjects with advanced ER+/HER2- BrCa

## Randomized Phase 2 Dose Expansion

- To evaluate the efficacy of GS-5829 in combination with fulvestrant compared to fulvestrant alone in subjects with advanced ER+/HER2- BrCa, as measured by overall response rate (ORR) and clinical benefit rate (CBR) evaluated according to Response Evaluation Criteria in Solid Tumors (RECIST) v. 1.1. ORR is defined as the proportion of subjects with response (complete response [CR], or partial response [PR]). CBR is defined as proportion of subjects with CR, PR, or stable disease (SD) that lasts for  $\geq 24$  weeks
- To evaluate the safety and tolerability of GS-5829 in combination with fulvestrant compared to fulvestrant alone in subjects with advanced ER+/HER2- BrCa
- To evaluate the overall survival (OS) for subjects with advanced ER+/HER2- BrCa who receive GS-5829 in combination with fulvestrant compared to fulvestrant alone

The exploratory objectives are as follows:

## 1.2. Study Design

### Phase 1b Dose Escalation:

In the study, cohorts of postmenopausal women with advanced ER+/HER2- BrCa, for whom no standard curative therapy exists and who are candidates for exemestane or fulvestrant, will be sequentially enrolled at progressively higher dose levels of oral GS-5829 in combination with standard doses of exemestane or fulvestrant. The starting dose of GS-5829 has been determined to be 4 mg once daily based on safety information, pharmacokinetic and biomarker data from two ongoing GS-5829 studies (GS-US-350-1599, GS-US-350-1604) and the recommendation by the Bayesian Logistic Regression Model (BLRM) of dose-dose limiting toxicity (DLT) relationship.

Eligible subjects will be assigned to either Group A or B based on prior treatment. Group A will initiate with GS-5829 orally once daily on Cycle 1 Day 1 (C1D1) combined with 25 mg of exemestane administered orally once daily (or in accordance with locally approved labeling). The subject may initiate exemestane any time prior to, or on, C1D1. Enrollment in Group A will be stopped after completion of the 4 mg GS-5829 dose level safety assessments. Subjects who were previously enrolled/treated in Group A will continue to be followed and managed.

Group B will initiate GS-5829 orally once daily on C1D1, with fulvestrant administered intramuscularly (in accordance with locally approved labeling) every 28 days ( $\pm 3$  days). The subject may initiate fulvestrant any time prior to, or on, C1D1. For subjects whom are treatment

naïve (in metastatic setting) and for all subjects for whom C1D1 is the subject's first dose of fulvestrant, a one-time additional dose of 500 mg fulvestrant should be administered on Cycle 1 Day 15 (C1D15).

Subjects may continue receiving GS-5829 once daily until disease progression (clinical or radiographic), unacceptable toxicity, withdrawal of consent, or death, whichever comes first. Following treatment discontinuation, subjects will be followed for safety for 30 days from the last dose of study drug.

Study procedures at screening, baseline, and during the study treatment and follow-up are outlined in the protocol and presented in [Appendix 1: Study Procedures Table](#) of this SAP.

